### 6.3.1.3 Interaction with Other Medications

**Drug-Drug Interactions:** Caution is recommended when administering Sorafenib together with compounds that are metabolized/ eliminated predominantly by the UGT1A1 pathway (e.g. irinotecan)

**Metabolism enzyme inducers** - A five-day application of rifampicin before taking a single dose of Sorafenib lead to a mean 37% decrease of the AUC of Sorafenib. Other inducers of CYP3A4 activity and/or glururonidation (e.g. Hypericum perforatum also known as St. John's wort, phenytoin, carbamazepine, phenobarbital, and dexamethasone) may increase metabolism of Sorafenib and thus decrease Sorafenib plasma concentrations.

**CYP3A4 Inducers** - Continuous concomitant administration of Sorafenib and rifampicin resulted in an average 37% reduction of Sorafenib AUC. Other inducers of CYP3A4 activity (e.g.

Hypericum perforatum also known as St. John's wort, phenytoin, carbamazepine, phenobarbital, and dexamethasone) may also increase metabolism of Sorafenib and thus decrease Sorafenib concentrations.

**CYP3A4 inhibitors** - Ketoconazole, a potent inhibitor of CYP3A4, administered once daily for 7 days to healthy male volunteers did not alter the mean AUC of a single 50 mg dose of Sorafenib. Therefore, clinical pharmacokinetic interactions of Sorafenib with CYP3A4 inhibitors are unlikely.

**CYP2C9 substrates** - The possible effect of Sorafenib on warfarin, a CYP2C9 substrate, was assessed in Sorafenib-treated patients compared to Placebo treated patients. The concomitant treatment with Sorafenib and warfarin did not result in changes in mean PT-INR compared to Placebo. However, patients taking warfarin should have their INR checked regularly (see section Warnings and Precautions for use).

**CYP isoform-selective substrates** - Concomitant administration of midazolam, dextromethorphan and omeprazole, which are substrates of cytochromes CYP3A4, CYP2D6 and CYP2C19, respectively, following 4 weeks of Sorafenib administration did not alter the exposure of these agents. This indicates that Sorafenib is neither an inhibitor nor an inducer of these cytochrome P450 isoenzymes.

**Combination with other anti-neoplastic agents** - In clinical studies, Sorafenib has been administered together with a variety of other anti-neoplastic agents at their commonly used dosing regimens, including gemcitabine, oxaliplatin, doxorubicin, and irinotecan. Sorafenib had no effect on the pharmacokinetics of gemcitabine or oxaliplatin. Concomitant use of paclitaxel (225 mg/m^2) and carboplatin (AUC = 6) with Sorafenib (100, 200 or 400 mg twice daily), administered with a 3-day break in dosing around administration of paclitaxel/carboplatin, resulted in no significant effect on the pharmacokinetics of paclitaxel. Concomitant treatment with Sorafenib resulted in a 21% increase in the AUC of doxorubicin. When administered with irinotecan, whose active metabolite SN-38 is further metabolized by the UGT1A1 pathway, there was a 67-120% increase in the AUC of SN-38 and a 26-42% increase in the AUC of irinotecan. The clinical significance of these findings is unknown. Docetaxel (75 or 100 mg/m^2 administered once every 21 days) when co-administered with Sorafenib (200 mg twice daily or 400 mg twice daily administered on Day 2 through 19 of a 21-day cycle), with a 3-day break in dosing, around administration of docetaxel, resulted in a 36-80% increase in docetaxel AUC and a 16-32%

increase in docetaxel  $C_{max}$ . Caution is recommended when Sorafenib is co-administered with docetaxel.

**Warfarin/ Phenprocoumon:** Infrequent bleeding events or elevations in the International Normalized Ratio (INR) have been reported in some patients taking warfarin while on Sorafenib therapy. Patients taking warfarin concomitantly should be monitored regularly for changes in prothrombin time, INR and for clinical bleeding episodes.

#### **6.3.1.4 Pregnancy and Lactation**

**Pregnancy:** It should be avoided becoming pregnant while on therapy. Women of childbearing potential must be apprised of the potential hazard to the fetus, which includes severe malformation (teratogenicity), failure to thrive and fetal death (embryotoxicity). Sorafenib should not be used during pregnancy. Prescribers may only consider it to be used, if the potential benefits justify the potential risks to the fetus.

- There are no adequate and well-controlled studies in pregnant women using Sorafenib. Studies in animals have shown reproductive toxicity including malformations. In rats, Sorafenib and its metabolites were demonstrated to cross the placenta and Sorafenib is anticipated to inhibit angiogenesis in the fetus.
- Women should avoid becoming pregnant while on therapy. Women of childbearing potential must be apprised of the potential hazard to the fetus, which includes severe malformation (teratogenicity), failure to thrive and fetal death (embryotoxicity). Women should use one safe method - like intrauterine pessary, hormonal treatment or vasoresection of the man + one additional method like diaphragm pessary or usage of condoms for birth control.
- In animals, Sorafenib has been shown to be teratogenic and embryotoxic. Adequate contraception should be used during therapy and for at least 3 months after completion of therapy.

**Breastfeeding** should be discontinued during Sorafenib therapy.

- It is not known whether Sorafenib is excreted in human milk. In animals, Sorafenib and/or its metabolites were excreted in milk. Because many drugs are excreted in human milk and because the effects of Sorafenib on infants have not been studied, woman should discontinue breastfeeding during Sorafenib treatment.

**Effects on fertility:** Results from animal studies indicate that Sorafenib can impair male and female fertility.

### 6.3.1.5 Adverse Reactions

The overall safety profile of Sorafenib is based on 1286 cancer patients, who received Sorafenib as single agent. This table will be used to determine the “expectedness” of ADRs used for reporting of adverse events to Regulatory Agencies from clinical studies. It is not a complete list of adverse events reported in clinical trials.

System Organ Class	Very Common > 10%	Common > 1% to < 10%	Uncommon > 0.1% to < 1%
Infections and infestations			Folliculitis infection
Blood and lymphatic system disorders	Lymphopenia	Leucopenia Neutropenia Anemia Thrombocytopenia	
Immune system disorders			Hypersensitivity reactions (including skin reactions and urticaria)
Endocrine disorders			Hypothyroidism
Metabolism and nutrition disorders	Hypophosphatemia	Anorexia	Hyponatremia Dehydration
Psychiatric disorders		Depression	
Nervous system disorders		Peripheral sensory neuropathy	Reversible posterior leukoencephalopathy*
Ear and labyrinth disorders		Tinnitus	
Cardiac disorders			Myocardial ischemia and infarction* Congestive heart failure*
Vascular disorders	Hemorrhage (including gastrointestinal* and respiratory tract* and cerebral hemorrhage*) Hypertension		Hypertensive crisis*
Respiratory, thoracic and mediastinal disorders		Hoarseness	Rhinorrhea
Gastrointestinal disorders	Diarrhea Nausea Vomiting	Constipation Stomatitis (including dry mouth and glossodynea) Dyspepsia Dysphagia	Gastro esophageal reflux disease Pancreatitis Gastritis Gastrointestinal perforation*
Hepato-biliary disorders			Increase in bilirubin and jaundice
Skin and subcutaneous tissue disorders	Rash Alopecia Hand-foot reaction** Pruritus Erythema	Dry skin Dermatitis exfoliativa Acne Skin desquamation	Eczema Erythema multiforme minor
Musculoskeletal, connective tissue and bone disorders		Arthralgia Myalgia	
Reproductive system and breast disorders		Erectile dysfunction	Gynaecomastia

General disorders and administration site conditions	Fatigue Pain (incl. mouth, abdominal, bone pain, headache and tumor pain)	Asthenia Fever Influenza-like illness	
Investigations	Increased amylase Increased lipase	Weight decreased Transient increase in transaminases	Transient increase in blood alkaline phosphatase INR abnormal, prothrombin level abnormal
* Events may have a life-threatening or fatal outcome. Such events are uncommon. ** Palmar plantar erythrodysesthesia syndrome in MedDRA			

Table 18: Adverse Drug Reactions in patients in multiple clinical trials (MedDRA coded)

In combination with cytotoxic agents, myelosuppression leading to febrile neutropenia has also been observed. Such events may have a life-threatening or fatal outcome.

The percent of patients experiencing treatment-emergent adverse events that were reported in at least 10% of patients who received Sorafenib versus Placebo on the phase- III RCC trial is shown in Table 19. CTCAE Grade 3 treatment-emergent adverse events were reported in 31% of patients receiving Sorafenib compared to 22% of patients receiving Placebo. CTCAE Grade 4 treatment-emergent adverse events were reported in 7% of patients receiving Sorafenib compared to 6% of patients receiving Placebo.

Adverse Event NCI-CTCAE v3 Category/Term	NEXAVAR N=451			Placebo N=451		
	All Grades %	Grade 3 %	Grade 4 %	All Grades %	Grade 3 %	Grade 4 %
Any Event	95	31	7	86	22	6
Cardiovascular, General						
Hypertension	17	3	<1	2	<1	0
Constitutional symptoms						
Fatigue	37	5	<1	28	3	<1
Weight loss	10	<1	0	6	0	0
Dermatology/ skin						
Rash/desquamation	40	<1	0	16	<1	0
Hand-foot skin reaction	30	6	0	7	0	0
Alopecia	27	<1	0	3	0	0
Pruritus	19	<1	0	6	0	0
Dry skin	11	0	0	4	0	0
Gastrointestinal symptoms						
Diarrhea	43	2	0	13	<1	0
Nausea	23	<1	0	19	<1	0
Anorexia	16	<1	0	13	1	0
Vomiting	16	<1	0	12	1	0
Constipation	15	<1	0	11	<1	0

Adverse Event NCI-CTCAE v3 Category/Term	NEXAVAR N=451			Placebo N=451		
	All Grades %	Grade 3 %	Grade 4 %	All Grades %	Grade 3 %	Grade 4 %
Hemorrhage/ bleeding						
Hemorrhage – all sites	15	2	0	8	1	<1
Neurology						
Neuropathy-sensory	13	<1	0	6	<1	0
Pain						
Pain, abdomen	11	2	0	9	2	0
Pain, joint	10	2	0	6	<1	0
Pain, headache	10	<1	0	6	<1	0
Pulmonary						
Dyspnea	14	3	<1	12	2	<1
Cough	13	<1	0	14	<1	0

Table 19: Treatment-Emergent Adverse Events Reported in at Least 10% of Sorafenib-Treated patients – Phase III Advanced RCC Study

The rate of adverse events (including events associated with progressive disease) resulting in permanent discontinuation was similar in both the Sorafenib and Placebo groups (10% of Sorafenib patients and 8% of Placebo patients).

Adverse Event* NCI-CTCAE v3 Category/Term	NEXAVAR N=297			Placebo N=302		
	All Grades %	Grade 3 %	Grade 4 %	All Grades %	Grade 3 %	Grade 4 %
Any Event	98	39	6	96	24	8
Constitutional symptoms						
Fatigue	46	9	1	45	12	2
Weight loss	30	2	0	10	1	0
Dermatology/ Skin						
Rash/ desquamation	19	1	0	14	0	0
Pruritus	14	<1	0	11	<1	0
Hand-foot skin reaction	21	8	0	3	<1	0
Dry skin	10	0	0	6	0	0
Alopecia	14	0	0	2	0	0
Gastrointestinal						
Diarrhea	55	10	<1	25	2	0
Anorexia	29	3	0	18	3	<1
Nausea	24	1	0	20	3	0
Vomiting	15	2	0	11	2	0
Constipation	14	0	0	10	0	0
Hepatobiliary/ pancreas						
Liver dysfunction	11	2	1	8	2	1
Pain						

Adverse Event* NCI- CTCAE v3 Category/Term	NEXAVAR N=297			Placebo N=302		
	All Grades %	Grade 3 %	Grade 4 %	All Grades %	Grade 3 %	Grade 4 %
Pain, abdomen	31	9	0	26	5	1

\*In study 100554 (HCC), the rate of ascites was similar in both NEXAVAR and Placebo groups.

Table 20: Adverse Events Reported in at least 10% of patients and at a higher rate in NEXAVAR-Arm than the Placebo Arm – Study 100554 (HCC)

Hypertension was reported in 9% of patients treated with NEXAVAR and 4% of those treated with Placebo. CTCAE grade 3 hypertension was reported in 4% of NEXAVAR treated patients and 1% of Placebo treated patients. No patients were reported with CTCAE grade 4 events in either treatment group.

Hemorrhage/ bleeding was reported in 20% of Placebo patients and 18% of those receiving NEXAVAR. The rates of CTCAE grade 3 and 4 bleeding was also higher in the Placebo group (CTCAE grade 3 in 5% Placebo and 3% NEXAVAR and CTCAE grade 4 in 4% Placebo and 2% NEXAVAR). Bleeding from esophageal varices was reported in 4% of Placebo treated patients and 2.4% in NEXAVAR treated patients.

Renal failure was reported in 2.6% of Placebo patients and 0.3% of those receiving NEXAVAR.

#### 6.3.1.6 Laboratory Abnormalities

The following laboratory abnormalities were observed in the phase III advanced RCC (TARGETS) trial:

**Elevated lipase and amylase:** Elevated lipase and amylase levels were very commonly reported. CTC Grade 3 or 4 lipase elevations occurred in 12% of patients in the Sorafenib group compared to 7% of patients in the Placebo group. CTC Grade 3 or 4 amylase elevations were reported in 1% of patients in the Sorafenib group compared to 3% of patients in the Placebo group. Clinical pancreatitis was reported in 2 of 451 Sorafenib treated patients (CTC Grade 4) and 1 of 451 patients (CTC Grade 2) in the Placebo group.

**Hypophosphatemia:** Hypophosphataemia was a common laboratory finding, observed in 45% of Sorafenib treated patients compared to 12% of Placebo patients. CTC Grade 3 hypophosphataemia (1–2 mg/dl) occurred in 13% on Sorafenib treated patients and 3% of patients in the Placebo group. There were no cases of CTC Grade 4 hypophosphataemia (< 1 mg/dl) reported in either Sorafenib or Placebo patients. The etiology of hypophosphataemia associated with Sorafenib is not known.

**Lymphopenia:** CTC Grade 3 or 4 were reported for lymphopenia in 13% of Sorafenib treated patients and 7% of Placebo patients, for neutropenia in 5% of Sorafenib treated patients and 2% of Placebo patients, for anemia in 2% of Sorafenib treated patients and 4% of Placebo patients and for thrombocytopenia in 1% of Sorafenib treated patients and 0% of Placebo.

**Anemia:** Observed in 44% of Sorafenib-treated patients and 49% of Placebo patients. CTCAE Grade 3 or 4 anemia was reported in 2% of Sorafenib-treated patients and 4% of Placebo patients.

**Thrombocytopenia:** Observed in 12% of Sorafenib-treated patients and 5% of Placebo patients. CTCAE Grade 3 or 4 thrombocytopenia was reported in 1% of Sorafenib-treated patients and 0% of Placebo patients.

Further details of the side effect profile of Sorafenib can be found in the current Nexavar® Prescribing Information (Fachinformation).

### **6.3.2 Standard cytotoxic therapy (Cytarabine and Daunorubicin)**

For information of all known adverse drug reactions please refer to the "Fachinformationsverzeichnis Deutschland" in its latest version.

## 7 STUDY OUTCOME AND STATISTICAL ANALYSIS

### 7.1 Power and Sample Size Calculation, Interim Analysis

Power calculations are based on the following assumptions:

Control group:	median event free survival (EFS) 9 months
Sorafenib group:	median event free survival (EFS) 13.5 months (improvement of 50%)
Error of first kind:	$\alpha = 0.05$ (two sided)
Power:	80%
Accrual time:	24 months
Follow up:	18 months
Randomization:	1/1 allocation

To detect an improvement of median EFS from 9 months to at least 13.5 months, we need 125 evaluable patients per group i.e. a total of 250 patients to yield the necessary number of approximately 191 events.

Although all efforts will be taken to avoid patient loss to follow up, there might be a rate of loss due to various possible reasons. Censoring by transplantation in first remission will lead to an additional loss. The rate of allogeneic transplantation is assumed with about 10% of the patients. Patients receiving allogeneic stem cell transplantation will be censored for analysis at the time point of transplant. In order to account for this, exponential hazard of 0.0074 is incorporated in the sample size calculation.

Within 24 months the participating centers are able to recruit up to 300 patients fulfilling the inclusion and exclusion criteria. Taking into account a drop out rate of about 10 % the study-centers will recruit the necessary number of patients (n=276) within 24 months.

All calculations are done using SAS-Software (PROC POWER) licensed to the University of Münster.

One interim analysis and the final analysis are planned for the intent-to-treat EFS endpoint such that the overall type I error is controlled at a two-sided 0.05 level. Interim analysis will be done according to the O'Brien/Flemming approach. When 50% of the expected intent-to-treat EFS events (191 events  $\times$  0.5 = 95) are attained the first interim analysis on the intent-to-treat EFS endpoint will be conducted.

The (unblinded) interim analysis will be performed by the Studienzentrale SAL in cooperation with Institut für Medizinische Informatik und Biometrie, Münster.

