### **3.3 Randomization Procedure and Stratification**

#### **3.3.1 Randomization**

The Studienzentrale SAL is responsible for the randomization process. The central randomization process will ensure allocation concealment. The randomization will be based on a randomization list containing randomization blocks. The use of randomization blocks guarantees equal numbers of patients in each treatment arm. In order to ensure equal proportions of patients from different strata in the two treatment arms, separate randomization lists for each stratum will be used (for description of strata, see below). Eligible study patients will be randomized by consecutive inclusion in the stratum-specific randomization list according to their cytogenetically or molecular defined stratum. Patients will be assigned one of the two treatment arms according to the randomization list (A or B).

The pharmacy in Dresden (Klinikapotheke des Universitätsklinikums Dresden) will assign treatment arms A or B to individual medication bottle numbers and will send the necessary supply of bottles to each participating center (see chapter 4.1.3, Drug accountability). A copy of the list containing medication numbers per center will be deposited at the Studienzentrale SAL.

Therefore, the Studienzentrale SAL will know which individual medication number corresponds with treatment arm A or B and will accordingly select and assign a medication bottle number to the randomized patient and add this number to the pre-existing patient study number. **The patient number plus the added three digits of the medication number will form the randomization number (Randomisationsnummer).** The Studienzentrale SAL will report the number to the recruiting center by fax. Figure 1 illustrates the general composition of the randomization number.

CCC – PPP – MMM

CCC = three digits for local trial center (Kliniknummer)

PPP = three digits for patient inclusion number

MMM = three digits for medication number

*Figure 1: Composition of the randomization number (Randomisationsnummer)*

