In order to ensure double blinding, the pharmacy will assign treatment arm A and B to Sorafenib or Placebo and neither the Studienzentrale SAL nor the investigators will know which treatment arm corresponds to Sorafenib and Placebo, respectively. The closed envelopes concealing the allocation of the individual patients will be deposited at the Dresden pharmacy and the local trial site only and not at the Studienzentrale. The Studienzentrale SAL will keep the randomization lists confidential and will not report the treatment arm to the investigators in order to ensure that in case of unblinding of one patient the investigator remains blinded for all other included and randomized patients. In case of unblinding, the investigators will have to contact the Safety Board which is separated from the randomization department at the Studienzentrale SAL. Even if the investigator reports the result of the unblinding to the Safety board, the results will not be reported to the randomization department. Therefore, in case of unblinding of an individual patient, the randomization department at SAL will still not be able to know which treatment arm corresponds with Placebo or Sorafenib and blinding throughout the whole trial period is guaranteed.

The centers will be supplied with starter medication kits after initiation of the study in the individual center. The center will report the eligible patient to the Studienzentrale SAL by faxing the patient registration form (Patientenmeldebogen) and send the required bone marrow and blood probes (Table 16, page 29) to the central laboratories (Table 17, page 29). After the Studienzentrale SAL has received the molecular and cytogenetic test results from the reference laboratories, the Studienzentrale SAL will perform the randomization as described above and

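### The protocol assigns the unblinded interim analysis to the Studienzentrale SAL, the A/B-list-holding office that section 3.3.1 says will not know which letter is Sorafenib

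*Protocol*

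**What the plan says.** Protocol section 3.3.1 puts allocation in one office: "The Studienzentrale SAL is responsible for the randomization process". The lists carry two letters only: "Patients will be assigned one of the two treatment arms according to the randomization list (A or B"). SAL can read the letter of every bottle, since "the Studienzentrale SAL will know which individual medication number corresponds with treatment arm A or B". The Dresden pharmacy alone decides which letter is active drug, and the section says of everyone else that "neither the Studienzentrale SAL nor the investigators will know which treatment arm corresponds to Sorafenib and Placebo, respectively". It adds that "The Studienzentrale SAL will keep the randomization lists confidential and will not report the treatment arm to the investigators", and closes its account of emergency unblinding with the statement that "blinding throughout the whole trial period is guaranteed".

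Section 7.1 plans one O'Brien-Fleming interim analysis of EFS at half of the 191 expected events, given as 95. It then says: "The (unblinded) interim analysis will be performed by the Studienzentrale SAL in cooperation with" the institute of medical informatics and biometry in Münster. It names no separate unblinded team and no route for the results.

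Other sections give SAL continuing operational work: the central safety desk (6.2), central data monitoring with its verification plan and query records (8.2), and the documentation assistants sent to sites (8.3). Section 8.1 has the DSMB meet quarterly with the coordinating investigator and be told of significant differences between arms.

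**The concern.** SAL's blind rests on a single fact, the meaning of two letters, because it already holds everything else. The protocol recognises how fragile this is: in 3.3.1 the result of one emergency unblinding is kept from SAL's randomisation department so that the letters stay undeciphered. Section 7.1 then gives SAL a comparison covering every randomised patient, with no matching protection.

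At stake is the conduct of the trial after the interim. People in the office that re-reviews the seriousness and relatedness of SAEs, directs source data verification and raises problematic cases at monitoring visits could know both the arms and the interim result. The EFS comparison is the confirmatory analysis (7.2), and two of its components, relapse and failure to reach CR/CRi (7.2.1), depend on assessment and documentation. A double-blind trial should not leave open who is blinded while its primary events are still accruing.

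**Working it through.** The point is a conflict between sections. Arithmetic serves only to show how much of the trial lies after the interim.

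**Sections side by side**

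| Question | 3.3.1 | 7.1 |
|---|---|---|
| Who holds the A/B lists? | SAL | – |
| Who knows each bottle's letter? | SAL | – |
| Who knows which letter is Sorafenib? | The pharmacy; not SAL, not the investigators | Whoever runs the unblinded interim, and SAL is named |
| Is any separation inside SAL stated? | Safety Board from randomisation department | None for the interim |

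- If the key is released to SAL, the letters on SAL's own lists become treatments for every patient, up to all 276 planned, and for list entries not yet used.
- If the key is not released, SAL still sees EFS for A against B. A clear difference, or the toxicity it sees through the safety desk, may suggest which letter is which.

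**Reproducing the plan's figures (7.1)**

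Inputs: medians 9 and 13.5 months, two-sided alpha 0.05, power 80%, 1:1 allocation, accrual 24 months, follow-up 18 months, loss hazard 0.0074. The protocol gives no time unit for the hazard; I read it as per month.

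Events (Schoenfeld): 4 × (1.960 + 0.842)² / (ln 1.5)² = 191, as stated. Half is 95.5; the plan uses 95. With uniform accrual and exponential EFS, 250 patients yield about 192 events by month 42, so N = 250 is also consistent.

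**Calendar time of the interim**

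For t up to 24 months, expected events are the sum over arms of

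(N/2)/24 × (λ/κ) × [t − (1 − e^(−κt))/κ], with λ = ln 2/median and κ = λ + 0.0074.

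- Control: λ = 0.0770, κ = 0.0844. Sorafenib: λ = 0.0513, κ = 0.0587.
- N = 250, t = 21.2: 53.8 + 41.2 = 95 events.
- N = 276: 95 events at t = 19.9.

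Patients still to be randomised are N × (24 − t − lag)/24, where the lag is the time from event 95 to the unblinded result. The protocol gives no lag, so it is an assumption shown as a range:

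| Assumed lag | N = 250 | N = 276 |
|---|---|---|
| 0 months | 29 | 47 |
| 2 months | 9 | 24 |
| 3 months | 0 | 12 |
| 4 months | 0 | 1 |

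With no lag, 191 − 95 = 96 primary events follow the interim. With a 2-month lag, about 110 events (N = 250) or 111 (N = 276) have occurred by then, leaving about 80 of the 191.

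**The case against.** The best defence has four parts.

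**The guarantee is narrower than it looks.** The sentence promising blinding throughout the trial concludes a passage on single-patient unblinding and refers to SAL's randomisation department. SAL is not one undivided office, and details of who sees interim data often sit in an SAP or DSMB charter. This stands for that sentence. It does not remove the conflict, because the same section says without qualification that SAL will not know the link, and 7.1 names SAL without qualification. A later document could specify a separation but could not make both statements true as worded.

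**Unblinded may mean by arm rather than pooled.** A two-sided log-rank test with a symmetric boundary can be run on A versus B without the key, and 7.1 does not say that the key is released. This is the less natural reading, but it makes full decoding conditional rather than certain.

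**A reader might infer that the double blind and allocation concealment collapse after the interim.** The documents do not support that. Lists are used consecutively within stratum, so SAL has no choice of arm. Sites register patients before randomisation, and SAL does not report arms to them. Patients and treating investigators stay blinded. No section gives SAL adjudication of EFS events, and the database is contracted to the KKS Dresden (8.3). What remains are the indirect routes: SAE review, queries and discussion of problematic cases.

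**A reader might take 29 to 47 patients as the expected number randomised by a decoded office.** It is an upper bound with no lag; the table above shows how quickly it shrinks.

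**Conclusion.** The contradiction between 7.1 and 3.3.1 is real, and carrying out 7.1 as written would break a blinding property that 3.3.1 states. If the key is released, every allocation on SAL's lists becomes readable to it, up to all 276. If not, SAL still sees the by-letter efficacy result. The consequence is an avoidable, indirect risk of bias in SAE review, monitoring queries and the handling of problematic cases after the interim. It is not a demonstrated failure of blinding at the bedside or of concealment at the sites.

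The timing figures rest on uniform accrual, exponential EFS at the planned medians and a monthly loss hazard. The conflict depends on none of them: even if accrual were complete at the interim, a large share of the primary events would still be to come.

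**What to change.** Reconcile the three sections.

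- **7.1:** state that the Münster institute, or another statistician with no role in randomisation, safety review or monitoring, alone receives the A/B key from the Dresden pharmacy and runs the interim. The protocol does not show that the Münster institute has no such role, so confirm this before naming it. SAL supplies the data and receives only the DSMB's recommendation.
- **8.1:** provide that by-arm results go to the DSMB in a closed session without the coordinating investigator. Otherwise the joint quarterly meeting, at which between-arm differences may be reported, reopens the same leak.
- **3.3.1:** cross-refer to 7.1, so that the statement about SAL's blinding and the interim procedure agree.

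The cost is a change of wording in three sections and one data-transfer step. If the Münster institute does not qualify, another independent statistician is needed.
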